Health-Related Quality of Life (HRQoL) will be evaluated with the validated Quality of Life questionnaires of the European Organization for Research and Treatment of Cancer (EORTC-QLQ), QLQ-C30 (30 items Core Quality of Life Questionnaire, version 3.0) and with the specific module for gastric cancer QLQ-STO22 (22 items Stomach Quality of Life Questionnaire).

- The EORTC-QLQ-C30 is a questionnaire that reflects the multidimensionality of HRQoL in patients with cancer. It is composed of 30 questions distributed in five functional scales (physical, role, cognitive, emotional and social), three scales of symptoms (fatigue, pain and nausea and vomiting), a global health scale and a series of additional questions to evaluate symptoms commonly referred by patients diagnosed with cancer (dyspnea, loss of appetite, insomnia, constipation and diarrhea) and the perceived financial impact.
- The EORTC-QLQ-STO22 questionnaire contains 22 structured items in five domains (dysphagia, food restrictions, pain, reflux and anxiety) and four specific items (dry mouth, alteration of taste perception, body image and hair loss) related to the symptoms of the disease.

Sample size

The calculation of the sample size is based on the primary objective of comparing fragile versus nonfragile patients with respect to postoperative mortality at 90 days after the intervention. Based on mortality data previously published in a retrospective study by Mosquera et al. (24), it is estimated that mortality for the group of non-frail patients is 0.6% and for the group with frailty 4.3%. From the data of the literature, a prevalence of 23% of frailty is calculated in the population of patients with gastric cancer and age \geq 70 years undergoing gastrectomy (24). For a power of 80% and a level of significance of 95% in a unilateral analysis, it is estimated that 276 non-fragile patients and 92 fragile patients would be needed to detect as statistically significant the difference between the proportion of patients who die between both groups.

Statistical analysis plan

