The characteristics of fragile and non-fragile patient groups will be compared through frequency tables. The Chi-square test will be used to compare the differences between the categorical variables and the ANOVA test for the continuous variables. Different analyzes are proposed according to the study variables that are to be analyzed. For dichotomous type response variables (90- day mortality, 12-month mortality, incidence of serious complications, incidence of in-hospital death in patients with complications, and hospital readmission at 30 days after discharge), a multivariate logistic regression will be used to evaluate the risk (odds ratio) of these variables. For continuous response variables (ICC score) at 30 days after the intervention, and number of days of hospital stay), linear regression models will be used. For the variable categorical response of the patient after hospital discharge, an ordinal logistic regression model will be done. All regression models will be adjusted for age, sex, body mass index (BMI), type of gastrectomy, center volume, neoadjuvant treatment and degree of frailty. Regarding HRQoL analysis, the mean scores and 95% confidence intervals for the different domains of preoperative HRQoL and one year after surgery will be calculated. Changes of more than 10 points on a scale from 0 to 100 will be considered clinically relevant as previously suggested in other publications (40). Work plan The study period includes: Patient recruitment. Follow-up for 1 year to meet the objectives of the study.

The study starts by assessing the fragility of the patients. Once the stage study is completed, the potential curative surgery is determined and after the case presentation in the Multidisciplinary Tumor Committee of each institution, the G8 questionnaires and modified fragility index will be carried out to identify the state and degree of fragility, 2 weeks prior to surgery. The result of the evaluation of the frailty of the patient, will be performed after the Multidisciplinary Committee, thus it will not modify the therapeutic decision.

To measure the Health Related Quality of Life (HRQoL), the QLQ-C30 and QLQ-STO22 questionnaires, will be delivered at the time of the preoperative visit and 12 months after surgery.

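### The study is sized on a one-sided 5% test, but the analysis plan states no sidedness, alpha or interval level for 90-day mortality; judged two-sided, power at 276/92 is about 64–70%, not 80%

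*Combined protocol and SAP*

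**What the plan says.** The Sample size section bases the calculation on the primary objective, frail against non-frail patients on 90-day mortality. It assumes that "mortality for the group of non-frail patients is 0.6% and for the group with frailty 4.3" per cent, and that "a prevalence of 23% of frailty is calculated in the population of patients with gastric cancer" aged 70 or over. The power, error rate and direction are given as "For a power of 80% and a level of significance of 95% in a unilateral analysis". The result is 276 non-frail and 92 frail patients. The calculation is described as a difference between two proportions, with no covariates.

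The Statistical analysis plan lists 90-day mortality among the dichotomous outcomes, for which "a multivariate logistic regression will be used to evaluate the risk (odds ratio) of these variables". The models are adjusted for age, sex, BMI, type of gastrectomy, centre volume, neoadjuvant treatment and degree of frailty. No direction, significance level or interval level is attached to the mortality analysis.

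Two nearby statements do not fill the gap. "The Chi-square test will be used to compare the differences between the categorical variables" stands in the text on the characteristics of the two groups, not on the primary outcome. The only interval level in the section, 95%, is for the quality-of-life means.

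**The concern.** The decision criterion for the single primary outcome appears only in the sample-size paragraph. The section that says how the outcome will be analysed uses a different method and does not say whether the frailty odds ratio is to be judged one-sided or two-sided.

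A result with a one-sided p-value between 0.025 and 0.05 would be positive under the sample-size criterion and negative under the usual two-sided reading of an odds ratio. Only about 5.6 deaths are expected (276 × 0.006 = 1.66 plus 92 × 0.043 = 3.96), so a single death can move the result across the line. The criterion should be fixed, where the analysis is specified, before the data are seen. The stated 80% also needs to describe the analysis that will be reported.

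**Working it through.** **Inputs (Sample size section).** p0 = 0.006 and n0 = 276 (non-frail); p1 = 0.043 and n1 = 92 (frail); difference d = 0.037. Assumption: the 95% significance level means alpha = 5%. The critical value is 1.645 one-sided and 1.960 two-sided. For 80% power, z = 0.842.

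**Step 1: the plan's own figure.** The documents do not name the formula. The pooled rate is (1.656 + 3.956)/368 = 0.01525. One formula that matches uses the pooled Poisson variance, 0.01525 × (1/n0 + 1/n1), with 3:1 allocation:

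n1 = (1.645 + 0.842)² × 0.01525 × (4/3) / 0.037² = 91.8, hence 92 frail and 276 non-frail.

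This agrees with the plan but does not prove that the formula was used. The usual two-proportion formula needs 364 + 122 = 486 patients for the same one-sided 80%.

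**Step 2: closed-form power at 276/92.**

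- Pooled Poisson: SE = √(0.01525 × (1/276 + 1/92)) = 0.01487 and d/SE = 2.489. One-sided: Φ(2.489 − 1.645) = 80.1%. Two-sided: Φ(2.489 − 1.960) = 70.2%.
- Usual formula: null SE = √(0.01525 × 0.98475 × (1/276 + 1/92)) = 0.01475; alternative SE = √(0.006 × 0.994/276 + 0.043 × 0.957/92) = 0.02165. One-sided: Φ((0.037 − 1.645 × 0.01475)/0.02165) = Φ(0.588) = 72.2%. Two-sided: Φ((0.037 − 1.960 × 0.01475)/0.02165) = Φ(0.373) = 64.6%.

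**Step 3: exact enumeration.** Each test is applied to every pair of binomial death counts, and the probabilities of the rejecting pairs are added. The likelihood-ratio and Wald rows are a logistic model with frailty as the only term; for Wald, a table with no deaths in one group counts as non-significant. The mid-p row uses 2.5% in the tested direction for its two-sided figure.

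| Method | One-sided 5% | Two-sided 5% | Loss (points) |
|---|---|---|---|
| Pooled Poisson formula | 80.1% | 70.2% | 9.9 |
| Usual two-proportion formula | 72.2% | 64.6% | 7.6 |
| Uncorrected chi-square, enumerated | 79.8% | 67.0% | 12.8 |
| Unadjusted logistic, likelihood ratio | 73.9% | 64.0% | 9.9 |
| Mid-p | 67.3% | 54.0% | 13.3 |
| Unadjusted logistic, Wald | 55.3% | 40.4% | 14.9 |
| Fisher, conventional two-sided | 61.2% | 61.2% | 0 |

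Fisher is unchanged because the opposite tail contributes essentially nothing at these sizes.

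**Step 4: separating the two causes.** By the usual formula, the step from 80% to 72.2% is choice of formula (7.8 points) and the step from 72.2% to 64.6% is sidedness (7.6 points). Only the second belongs to the one-sided assumption.

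**Step 5: how secure is the 79.8%?** At 276/92 the enumerated one-sided chi-square has a true type I error of about 8% when both groups have 1.5% mortality and about 12% at 0.6%. Part of its power therefore comes from exceeding 5%, and its 12.8-point loss should be read with that in mind.

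**The case against.** The strongest reply is that nothing conflicts. The Sample size section ties a one-sided criterion to the primary objective by name, the analysis plan follows directly and names the model, and a logistic coefficient can be tested one-sided. This reply stands against a stronger claim that a reader might infer, that the 80% belongs to a test that will not be run. The documents do not show that: the analysis plan is silent on sidedness, and reading an odds ratio two-sided is convention rather than plan text.

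A reader might also take the chi-square sentence or the 95% intervals as proof of a two-sided primary test. Neither is. The first concerns group characteristics and the second quality of life.

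It is fair, too, that sidedness costs nothing by the conventional Fisher test, a serious candidate with so few deaths, so the loss is not universal. Finally, none of the powers above is for the covariate-adjusted model, so a restated 65% is also an approximation to the planned analysis.

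The omission remains. A criterion given only in a sample-size paragraph, for a different method, does not tell the analyst how to judge the odds ratio. And the planned type of model, even unadjusted, does not reach 80% on the one-sided reading: 74% by likelihood ratio and 55% by Wald.

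**Conclusion.** The point holds as an omission with a measurable consequence, not as a contradiction. The plan does not carry its one-sided 5% criterion into the analysis of 90-day mortality. If the odds ratio is judged two-sided at 5%, power at 276/92 is about 64–70% by the usual formula, enumerated chi-square, unadjusted likelihood-ratio test or pooled Poisson formula; it is 54% by mid-p, 40% by Wald and 61% by Fisher. Sidedness accounts for roughly 8 to 13 points by the chi-square, likelihood-ratio, Poisson, usual-formula and mid-p calculations. It would be wrong to attribute the whole fall from 80% to about 65% to sidedness, since about half of it, by the usual formula, is choice of formula.

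This rests on the plan's mortality rates and group sizes, on reading the significance level as alpha = 5%, and on unadjusted calculations. The power of the adjusted model was not computed, because the documents give no covariate effects.

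**What to change.** - **Statistical analysis plan:** state that the effect of frailty on 90-day mortality is judged by a two-sided 5% test, with a 95% confidence interval for the odds ratio.
- **Sample size:** replace 80% by the power for that test at 276/92, about 65%, labelled as an unadjusted approximation and with the method named.
- **Alternative:** if the sponsor keeps the one-sided 5% test, say so in the Statistical analysis plan, report the matching 90% interval, and give the one-sided power of the chosen method (about 72–74% by the usual formula or the unadjusted logistic likelihood-ratio test).

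The cost is two sentences and a less favourable stated power. No extra patients or data are needed.

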Primary and secondary variables The impact of the frailty on different outcome variables will be evaluated. The main outcome variable will be 90-day mortality after the intervention. Other secondary outcome variables will also be evaluated: incidence of serious complications (Clavien-Dindo complications score ≥ 3), Complication Comprehensive Index (CCI) score (37, 38), hospital stay, incidence of death in patients suffering from a complication (failure to-rescue), hospital readmission within the first 30 days after the discharge, destination of the patient after discharge from hospital [home, social health centers, or geriatric residence], mortality at 12 months after the intervention, quality of life before the intervention and at 12 months.

Frailty evaluation For the assessment of frailty (frailty screening), two questionnaires will be used:

- Questionnaire G8: This is a questionnaire with 8 questions, easy to use, with a total score that varies from 0 to 17 points. Previous studies suggest the score ≤ 14 as a cut-off point to identify the fragile patient, with a sensitivity of 92% and specificity of 52% (36).
- Modified frailty index: This index was described by Velanovich et al. (14), based on a previously validated simplification of the frailty index CSHAFI (Canadian Study of Health and Aging Frailty Index), which was specifically designed to analyze data included in the National Surgical Quality Improvement Program of the American College of Surgeons (ACSNSQIP). It consists of 11 questions with 1 point assigned to each of them on the functional, endocrine, respiratory, cardiovascular and neurological status of the patient. It allows to divide the patients into 4 groups: without frailty (FI = 0), slightly fragile (FI = 1), moderately fragile (FI = 2) and severely fragile (FI ≥ 3).

Postoperative complications Postoperative complications will be classified according to the recommendations proposed by the European Chapter of the International Gastric Cancer Association (EGCA) (unpublished data), its severity through the classification of Clavien-Dindo and the CCI (37, 38). In particular, the CCI will be calculated using the free application that can be found on the website: www.assessurgery.com/calculator_single/.

[Health-related quality of life](#)

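### The adjusted logistic model for 90-day mortality expects 5.6 deaths for at least seven coefficients; with binary frailty at the planning rates its odds ratio is not finite in 20.4% of trials, and the stated 80% power belongs to an unadjusted test

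*Combined protocol and SAP*

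**What the plan says.** The Sample size section states the "primary objective of comparing fragile versus nonfragile patients with respect to postoperative mortality at 90 days after the intervention". It sets the rates: "it is estimated that mortality for the group of non-frail patients is 0.6% and for the group with frailty 4.3" per cent. The error rates are given as "For a power of 80% and a level of significance of 95% in a unilateral analysis", and the result is that "276 non-fragile patients and 92 fragile patients would be needed to detect as statistically significant the difference" between the two proportions. Covariates play no part in this calculation.

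The Statistical analysis plan handles 90-day mortality differently. It is listed first among the dichotomous outcomes for which "a multivariate logistic regression will be used to evaluate the risk (odds ratio) of these variables". The plan adds: "All regression models will be adjusted for age, sex, body mass index (BMI), type of gastrectomy, center volume, neoadjuvant treatment and degree of frailty". The chi-square test in the same section is introduced for comparing the characteristics of the two groups.

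Two instruments appear under Frailty evaluation. For the G8, "Previous studies suggest the score ≤ 14 as a cut-off point to identify the fragile patient". For the modified frailty index (mFI), "It allows to divide the patients into 4 groups". The documents do not say which of these defines a frail patient in the primary comparison, or how degree of frailty is coded in the model.

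They also give no expected number of deaths, no rule for a group without deaths, no named test for the regression coefficient and no power for the adjusted model.

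**The concern.** The sample size rests on a two-group difference in proportions, but the outcome is to be analysed with an adjusted logistic model. The planned death rates are so low that the choice between these methods matters.

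With a handful of deaths, one frailty group may have none. Ordinary maximum likelihood then gives no finite frailty odds ratio, whatever the other covariates are. The analyst would have to choose a remedy after seeing the deaths, and that choice affects both the estimate and the p-value. The power quoted to justify the study would also belong to a test the plan does not use for its main outcome.

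**Working it through.** **Inputs.** From the Sample size section: 276 non-frail and 92 frail patients, death rates of 0.6% and 4.3%, one-sided, 80% power. The 95% significance level is read as a 5% type I error. From the Statistical analysis plan: six covariates plus degree of frailty. That makes at least seven coefficients besides the intercept, or nine if the four mFI groups enter as categories.

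**1. The plan's own figure.** Exact binomial enumeration of an uncorrected, unadjusted one-sided Pearson test at 276/92 gives power of 79.8%, matching the stated 80%. The smallest 3:1 sample reaching 80% is 279/93. The usual normal formula gives 72.2% and the one-sided Fisher test 61.2%. The Pearson test is therefore inferred from the match; the protocol does not name it. Its exact type I error at a common mortality of 5.612/368 = 1.525% is 8.1%.

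**2. Expected deaths.** 276 × 0.006 + 92 × 0.043 = 1.656 + 3.956 = 5.61. Per coefficient this is 5.61/7 = 0.80, or 5.61/9 = 0.62. The chance of seven or fewer deaths is 79.8%.

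**3. A group with no deaths.**
- Non-frail: 0.994^276 = 0.1900.
- Frail: 0.957^92 = 0.0175.
- Both: 0.1900 × 0.0175 = 0.0033.
- Either: 0.1900 + 0.0175 − 0.0033 = 0.2042.

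The 20.4% divides into an infinite odds ratio (18.7%), a zero odds ratio (1.4%) and no deaths at all (0.3%). Adding covariates cannot make the frailty estimate finite in these trials, so 20.4% is a floor for the adjusted model with binary frailty. A 4,000-trial simulation with six assumed covariates unrelated to death put it almost at the floor: 19.7% non-finite, against 19.6% with an empty group in the same runs.

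**4. Power of the candidate tests.** Unadjusted, one-sided 5%, exact enumeration, 276/92. A Wald test without a finite estimate counts as not significant.

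| Both rates multiplied by | Expected deaths | A group with no deaths | Pearson | Likelihood ratio | Firth | Wald |
|---|---|---|---|---|---|---|
| 0.75 | 4.21 | 32.3% | 73.3% | 64.6% | 60.3% | 37.2% |
| 1 | 5.61 | 20.4% | 79.8% | 73.9% | 72.6% | 55.3% |
| 1.25 | 7.01 | 13.1% | 85.1% | 81.2% | 80.8% | 68.7% |
| 1.5 | 8.42 | 8.4% | 89.2% | 86.5% | 86.4% | 78.3% |
| 2 | 11.22 | 3.6% | 94.5% | 93.4% | 93.4% | 89.8% |

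Type I error at a common 1.525% mortality is 8.1% (Pearson), 5.8% (likelihood ratio), 5.3% (Firth) and 4.7% (Wald).

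**5. Adjusted power, by simulation.** There were 2,000 trials per setting, with Monte Carlo error of about 1 point. Age and BMI were assumed normal, and the other four covariates binary with 40% prevalence. Firth power at the planning rates is 71.0% if the covariates are unrelated to death. It is 60.7% or 55.4% if frail patients are assumed to be 0.5 SD older and the death odds rise 1.5 or 2.0 times per SD of age, with group death rates held fixed. The adjusted frailty odds ratio is then 6.1 or 5.4 instead of 7.4. Type I error is 5.7% without and 5.1% with confounding.

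**6. Other codings of frailty.** These use assumed mFI level sizes. A linear four-level term is non-finite in 4–6% of trials if an index of 2 or more counts as frail, and in 18–19% if only 3 or more does. With four categories, some level has no deaths in 77–98% of trials.

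**The case against.** The strongest objection is that the planning rates may be too low. The Introduction says the published frailty studies generally analyse 30-day mortality, and the study supplying 0.6% and 4.3% is among those it cites. Deaths by day 90 cannot be fewer than deaths by day 30. At 1.5 times the rates the non-finite share falls to 8.4%, and likelihood-ratio power passes 80%. This stands as a limit on the size of the problem. It does not remove it: a plan should work at its own assumptions, and at rates a quarter lower the share is 32.3%.

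Second, a group without deaths is a feature of the two-by-two table and is not caused by the number of covariates. Unadjusted Firth power is 72.6%, and adding covariates unrelated to death lowers it only to 71.0%. This is correct. The count of seven coefficients shows how little information there is, but the 20.4% does not come from it.

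Third, the 20.4% assumes binary frailty, while the model term is called degree of frailty. Binary is the comparison used for sizing, and the open coding is part of the defect.

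Fourth, in the 18.7% of trials with deaths only among frail patients, the unadjusted one-sided likelihood-ratio test is always significant at 5%, though only just at 0/276 v 1/92 (z = 1.67). So a p-value can be had. But the plan promises an odds ratio, names no test, and would still have no finite estimate.

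Fifth, the confounded power figures of 61% and 55% rest on assumed inputs, and part of the drop reflects a smaller adjusted effect. They serve only as a sensitivity range.

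**Conclusion.** The concern holds and should be corrected before analysis. With binary frailty at the protocol's rates and group sizes, the analysis of the main outcome as written yields no finite frailty odds ratio in 20.4% of trials. The stated 80% is not the power of that analysis. Even without adjustment, one-sided logistic power is 73.9% or 55.3%, depending on a test the plan leaves open.

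The expected deaths, the 20.4% and the unadjusted power figures are exact given the planning inputs. The adjusted power and the results for other frailty codings depend on stated assumptions. If true death rates are 1.5 times the planning rates, likelihood-ratio or Firth power is adequate (about 86% unadjusted), but 8.4% of trials would still lack a finite odds ratio.

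**What to change.** In the Statistical analysis plan, for 90-day mortality:
1. State that the primary frailty term is the binary frail/non-frail comparison used for sizing, and name the instrument and cut-off that define it.
2. Prespecify Firth penalised logistic regression with a penalised profile-likelihood interval and test, keeping the planned covariates.
3. Report the absolute risk difference with an exact or score interval beside the odds ratio.

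In the Sample size section, replace 80% with the power of that analysis and state its assumptions. At 276/92 and one-sided 5% it is roughly 70% if the covariates are unrelated to death. Add a sensitivity range for confounding and for other death rates. Apply the same method to failure-to-rescue if its deaths are similarly few.

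The cost is SAP wording, a standard software option and one restated figure, with three drawbacks:
- **Shrinkage.** Firth pulls the odds ratio towards 1. At 2/276 v 4/92 it goes from 6.2 to 5.6 (about 10%), and at 1/276 v 4/92 from 12.5 to 9.3 (about 25%).
- **No added information.** At 0/276 v 4/92 Firth gives 28.1 with a 95% interval of 3.0 to about 3,700. The estimate is finite but very imprecise.
- **Lower stated power.** At the planning rates, the figure for the same sample size will be less favourable.

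### The linear models for hospital stay and the 30-day complication index name no variance estimator; with unequal frailty groups, default 95% intervals for the frailty effect can miss their stated coverage.

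*Combined protocol and SAP*

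**What the plan says.** All references are to the combined protocol and SAP.

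- **Model.** The Statistical analysis plan section introduces the two outcomes with "For continuous response variables (ICC score) at 30 days after the intervention" and continues "number of days of hospital stay), linear regression models will be used". The index is the comprehensive complication index listed under Primary and secondary variables.
- **Covariates.** "All regression models will be adjusted for age, sex, body mass index (BMI), type of gastrectomy, center volume, neoadjuvant treatment and degree of frailty".
- **Group sizes.** The Sample size section plans "276 non-fragile patients and 92 fragile patients", from a calculation for 90-day mortality. It also states that "a prevalence of 23% of frailty is calculated in the population of patients with gastric cancer".
- **Frailty definition.** Frailty evaluation describes two instruments, G8 with a cut-off of 14 and a modified frailty index with four grades. It does not say which one defines the two-group comparison.
- **Not stated.** No section gives a standard-error method, a transformation, a residual check or a fallback model for these regressions. No SD, expected difference or power is given for stay or the index. Confidence intervals are named only for the quality-of-life means.

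**The concern.** Linear regression without further specification is normally run as least squares with one common residual variance. The standard error of the frailty effect then rests on a pooled variance, to which the larger group contributes most. If the smaller group is the more variable, that standard error is too small.

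The study gives reason to expect this. The Introduction cites evidence that frailty goes with more complications and longer stay, and the planned frail group is a third the size of the non-frail group. For a non-negative, right-skewed outcome, a higher mean usually brings a larger spread.

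The estimated mean difference stays valid. What is at risk is the interval around it, for two secondary outcomes that bear on the morbidity and hospital stay named in the Objective.

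**Working it through.** The plan has no figure of its own for these outcomes to reproduce. The check therefore takes the group sizes from the plan and assumes the spread.

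**Inputs.** From the Sample size section: 92 frail and 276 non-frail, total 368. Assumed: r, the ratio of frail to non-frail SD; for stay, a lognormal shape with median 12 days, log SD 0.6 to 0.8, and frailty multiplying stay by k.

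**Step 1: pooled against true standard error, two groups.**

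Ratio = sqrt{ [(91r² + 275)/366] × (1/92 + 1/276) ÷ (r²/92 + 1/276) }

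Coverage of a nominal 95% interval = 2Φ(1.96 × ratio) − 1

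| r | pooled/true SE | coverage |
|---|---|---|
| 1 | 1.000 | 95.0% |
| 1.25 | 0.895 | 92.1% |
| 1.5 | 0.823 | 89.3% |
| 2 | 0.733 | 84.9% |

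A simulation with frailty and six covariates (6,000 data sets per setting) gave 92.1%, 88.8% and 85.0% for r = 1.25, 1.5 and 2 with normal errors, and 92.4%, 89.1% and 84.9% with lognormal errors. HC3 errors gave 94.9%, 94.8% and 95.0%, and 94.7%, 94.4% and 94.0%.

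**Step 2: tie r to a frailty effect on stay.** If frailty multiplies a lognormal stay by k, it multiplies the SD by k as well, so r = k.

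- k = 1.3: pooled variance (91 × 1.69 + 275)/366 = 1.172. Ratio = sqrt(1.172 × 0.01449 ÷ 0.02199) = 0.879, coverage 91.5%.
- k = 1.5: ratio 0.823, coverage 89.3%.

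Simulation (20,000 lognormal data sets per setting) gave pooled coverage of 91.8% for k = 1.3 at log SD 0.6 and at 0.8, and 89.2% for k = 1.5 at log SD 0.8. Robust coverage was 93.8 to 94.7%.

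**Step 3: the null case.** With k = 1 the two groups have the same mean and the same variance. Simulated two-sided type I error was 5.1% (log SD 0.6) and 4.9% (log SD 0.8) with pooled errors, and 5.4% and 5.7% with HC3-type errors.

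**Step 4: a different split.** Frailty evaluation quotes sensitivity 92% and specificity 52% for G8 ≤ 14. Assume these apply here and that true prevalence is the planned 23%. G8 then flags 0.23 × 0.92 + 0.77 × 0.48 = 0.212 + 0.370 = 58%, or about 214 of 368, leaving 154 non-frail. With 214 and 154 in the Step 1 formula, the ratio is 1.04, 1.07 and 1.10 for r = 1.25, 1.5 and 2, and coverage is 95.8%, 96.3% and 96.9%. With equal groups (184 each), coverage is 95.0% at every r.

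**Step 5: what robust errors cost.** At 92 v 276, the large-sample widening is 1/0.879 = 1.14 for k = 1.3 and 1/0.823 = 1.22 for k = 1.5. In simulated lognormal data it is about 12 to 21%. At log SD 0.8 and k = 1.3, power falls from about 67% with pooled errors to about 60% with robust ones. A log-scale analysis there has about 78%.

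**The case against.** **The plan does not say constant variance.** This is correct. A reader might infer that the plan has chosen constant-variance standard errors, but it is silent. Its use of ANOVA for continuous characteristics suggests conventional defaults without settling the matter. The point is therefore an unguarded default, not a stated wrong choice.

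**False positives.** A reader might infer that type I error rises to 7.9%, 10.7% or 15.1%, which is what Step 1 implies for r = 1.25, 1.5 and 2 (100% minus coverage). Those figures need equal means with unequal SDs. If variance differs only because it follows the mean, no frailty effect means no difference in variance, and Step 3 shows the default test holding its level. Nothing in the documents supports the other scenario.

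**Direction.** A reader might infer that the intervals must be too narrow. That depends on the frail group being the smaller one. The 92 v 276 split rests on a planning prevalence, and Step 4 shows that the plan's own G8 figures could reverse the direction. Degree of frailty may also enter at four levels, which the two-group formula does not represent. This objection stands, but it does not favour the default: robust errors correct either direction.

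**No distributions are given.** This stands. The size for stay is conditional on the assumed lognormal shape. For the complication index, no distribution was modelled; a floor makes a similar pattern plausible and no more.

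**No interval is promised for these models.** This is true, but any interval or p-value reported from them uses the same standard error.

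**Conclusion.** The concern holds as a conditional statement about interval coverage. If stay is roughly lognormal, frailty lengthens it by 1.3 to 1.5 times and the 92 v 276 split is realised, default 95% intervals fall about 3 to 6 percentage points short of their stated coverage. If the frail group turns out larger, they over-cover by about 1 to 2 points at SD ratios of 1.25 to 2. If the variances or the group sizes are equal, there is no error of this kind.

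The documents do not support a claim of general type I error inflation, a fixed direction of error, or a measured size for the complication index. The 90-day mortality analysis is untouched. The change is worth making because it is cheap and works whichever way the split falls.

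**What to change.** Keep the linear models, which estimate the mean difference. Add one sentence to the Statistical analysis plan section: standard errors, confidence intervals and p-values for hospital stay and the complication index will be heteroscedasticity-robust (HC3) or from a bootstrap.

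Log-transformed stay may be added as an optional supporting analysis. It estimates a different quantity, the ratio of geometric means, and its power advantage in Step 5 assumes lognormal data, so it should not replace the difference in days.

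The cost is one sentence and one software option, with no new data or patients. Intervals widen, and some nominal power is lost, by the amounts in Step 5. If the variances are equal, almost nothing changes.
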